APPENDIX 6 DIAGNOSTIC CRITERIA FOR DRUG AND ALCOHOL ABUSE

The following is taken from DSM-IV:

Diagnostic Criteria for Psychoactive Substance Dependence

A maladaptive pattern of substance use, leading to clinically significant impairment or distress as manifested by three (or more) of the following, occurring at any time in the same 12-month period:

1. Tolerance, as defined by either of the following:
 - a) A need for markedly increased amounts of the substance to achieve intoxication or desired effect,
 - b) Markedly diminished effect with continued use of the same amount of the substance.
2. Withdrawal, as manifested by either of the following:
 - a) The characteristic withdrawal syndrome for the substance,
 - b) The same (or closely related) substance is taken to relieve or avoid withdrawal symptoms.
3. The substance is often taken in larger amounts or over a longer period than was intended.
4. There is a persistent desire or unsuccessful efforts to cut down or control substance use.
5. A great deal of time is spent in activities necessary to obtain the substance (eg, visiting multiple doctors or driving long distances), use the substance (eg, chain-smoking) or recover from its effects.
6. Important social, occupational or recreational activities are given up or reduced because of substance use.
7. The substance use is continued despite knowledge of having a persistent or recurring physical or psychological problem that is likely to have been caused or exacerbated by the substance (eg, current cocaine use despite recognition of cocaine-induced depression, or continued drinking despite recognition that an ulcer was made worse by alcohol consumption.)

Criteria for Severity of Psychoactive Substance Dependence:

Mild: Few, if any, symptoms in excess of those required to make the diagnosis, and the symptoms result in no more than mild impairment in occupational functioning or in usual social activities or relationships with others.

Moderate: Symptoms or functional impairment between “mild” and “severe”.

Severe: Many symptoms in excess of those required to make the diagnosis, and the symptoms markedly interfere with occupational functioning or with usual social activities or relationships with others.

In Partial Remission: During the past six months, some use of the substance and some symptoms of dependence.

Clinical Protocol
BMS-986177

CV010010
FXIa

In Full Remission: During the past six months, either no use of the substance, or use of the substance and no symptoms of dependence.

Diagnostic Criteria for Psychoactive Substance Abuse

- A. A maladaptive pattern of psychoactive substance use, leading to clinically significant impairment or distress as manifested by one (or more) of the following, occurring at any time in the same 12-month period:
1. Recurrent substance use resulting in a failure to fulfill major role obligations at work, school, or home (e.g., repeated absences or poor work performance related to substance use; substance-related absences, suspensions, or expulsions from school, neglect of children or household).
 2. Recurrent substance use in situations in which it is physically hazardous (eg, driving an automobile or operating a machine when impaired by substance use).
 3. Recurrent substance-related legal problems (eg, arrests for substance-related disorderly conduct).
 4. Continued substance use despite having persistent or recurrent social or interpersonal problems caused or exacerbated by the effects of the substance (eg, arguments with spouse about consequences of intoxication, physical fights).
- B. The symptoms have never met the criteria for substance dependence for this class of substance.

Clinical Protocol
BMS-986177

CV010010
FXIa

[REDACTED]

[REDACTED]

[REDACTED]

[REDACTED]

[REDACTED]

SUMMARY OF KEY CHANGES OF REVISED PROTOCOL 02		
Section Number & Title	Description of Change	
Title Page	Updated study director/medical monitor.	
2 Schedule of Activities (SOA)	Duplicate row for pregnancy test was deleted and the Day 8 pregnancy test was moved to Day 13 to 15/Study Discharge column and clarified for WOCBP only. Clarified vital signs, stool occult blood, whole blood for genotyping/ADME, and SAEs.	
2 SOA and 9.4.4 Clinical Safety Laboratory Assessments	Clarified urine dipstick for blood only if the participant is able to produce urine. Clarified that the pregnancy test is for WOCBP only.	
2 Schedule of Activities (SOA) 5.1 Overall Design	Updated the screening window from 21 days to 28 days.	
5.2 Number of Participants	Clarified the target sample size of 32 participants is to achieve 24 participants who complete the 4 study treatments.	

Revised Protocol No.: 03
Date: 06-Sep-2017

SUMMARY OF KEY CHANGES OF REVISED PROTOCOL 02		
Section Number & Title	Description of Change	
6.2 Exclusion Criteria	Clarify prior aspirin use to at least 1 week before dosing in exclusion criteria 2a. Updated duration contraceptive methods to be used for men in exclusion criteria 3e.	
7.7.1 Prohibited and/or Restricted Treatments	Clarify concomitant use of NSAIDS or aspirin to within 1 week prior to study drug administration. Also allow the use of topical antifungals.	
9.5 Pharmacokinetics	Extraction ratio was deleted	
9.7.1 Genotyping and ADME Sampling	Clarify that whole blood sample to be drawn at baseline for dosed participants.	
Appendix 4 WOCBP Definitions and Methods of Contraception	Requirements for WOCBP participants to use one highly effective and/or one less effective method of contraceptive has been added. Duration of contraceptive methods for males has been updated to align with updating exclusion criteria 3e.	
Title Page	Updated study director/medical monitor.	
2 Schedule of Activities (SOA)	Duplicate row for pregnancy test was deleted and the Day 8 pregnancy test was moved to Day 13 to 15/Study Discharge column and clarified for WOCBP only. Clarified vital signs, stool occult blood, whole blood for genotyping/ADME, and SAEs.	

SUMMARY OF KEY CHANGES OF REVISED PROTOCOL 02		
Section Number & Title	Description of Change	Brief Rationale
2 SOA and 9.4.4 Clinical Safety Laboratory Assessments	Clarified urine dipstick for blood only if the participant is able to produce urine. Clarified that the pregnancy test is for WOCBP only.	Clarification added based on feedback from a site that many of the end stage renal disease patients (ESRD) are unable to produce urine.
2 Schedule of Activities (SOA) 5.1 Overall Design	Updated the screening window from 21 days to 28 days.	Being a hemodialysis patient study, flexible in the screening period is needed to schedule the study with the participant's hemodialysis schedule.
5.2 Number of Participants	Clarified the target sample size of 32 participants is to achieve 24 participants who complete the 4 study treatments.	It was not intended to achieve 24 evaluable participants as previously written which would be those who received 1 dose of study drug.
6.2 Exclusion Criteria	Clarify prior aspirin use to at least 1 week before dosing in exclusion criteria 2a. Updated duration contraceptive methods to be used for men in exclusion criteria 3e.	Updated based on review of screen failures and the change will not likely impact the study assessment or patient safety. Definitive embryo-fetal development (EFD) studies have been completed and findings from these studies indicate that BMS-986177 is non-terogenic and non-genotoxic.
7.7.1 Prohibited and/or Restricted Treatments	Clarify concomitant use of NSAIDs or aspirin to within 1 week prior to study drug administration. Also allow the use of topical antifungals.	Updated based on review of screen failures. These changes will not likely impact the study assessment or patient safety.
9.5 Pharmacokinetics	Extraction ratio was deleted	It was a duplication to %DR (Percent dose of BMS-986177 recovered in dialysate %).
9.7.1 Genotyping and ADME Sampling	Clarify that whole blood sample to be drawn at baseline for dosed participants.	To make this consistent with Section 2 Schedule of Activities (SOA).
Appendix 4 WOCBP Definitions and Methods of Contraception	Requirements for WOCBP participants to use one highly effective and/or one less effective method of contraceptive has been added. Duration of contraceptive	Appendix has been updated to reflect the latest protocol model template. Definitive embryo-fetal development (EFD) studies have been completed and findings from these studies indicate that BMS-986177 is non-terogenic and non-

SUMMARY OF KEY CHANGES OF REVISED PROTOCOL 02		
Section Number & Title	Description of Change	Brief Rationale
	methods for males has been updated to align with updating exclusion criteria 3e.	genotoxic.

SUMMARY OF KEY CHANGES FOR REVISED PROTOCOL 01		
Section Number & Title	Description of Change	
Section 3.3: Benefit/Risk Assessment	Safety data was updated from FIH SAD/MAD study (CV010001). Also, the safety data from the HD PK study (CV010012) was added.	
Section 5.1: Overall Design	BMS dose 1 and BMS dose 2 were updated to be BMS-986177 100 mg and BMS-986177 300 mg, respectively. Other minor changes made in this section.	
Section 5.5: Justification for Dose	Updated targeted exposures based on hemodialysis PK study to support the BMS dose 1 (100 mg) and BMS dose 2 (300 mg)	
Section 6.2: Exclusion Criteria and Section 6.3: Lifestyle Restrictions	Exclusion criteria 1a, 1d, 1i, 1n, 3b, and 3e were clarified. Exclusion criterion 2b was added. Restrictions were updated.	
Section 7: Treatment	BMS-986177 100 mg and 300 mg (to replace BMS dose 1 and dose 2) were added to Table 7.-1 and Table 7.1-1.	
Section 7.2: Method of Treatment	Reference to IRT was removed.	

SUMMARY OF KEY CHANGES FOR REVISED PROTOCOL 01		
Section Number & Title	Description of Change	
Assignment and Section 7.3: Blinding		
Section 7.7.1: Prohibited and/or Restricted Treatments	Prohibited/restricted treatments were updated.	
Section 8.1: Discontinuation from Study Treatment	Updated the discontinuation criteria on events of complete clotting of hemodialysis circuit to include enoxaparin treatment arm and 5 or more patients.	
Section 9.5: Pharmacokinetics	Updates to further clarify Table 9.5-1 were made.	
Section 9.6: Pharmacodynamics	Updates to further clarify Table 9.6-1 and Table 9.6-2 were made.	
Section 9.8: Biomarker	Updates to further clarify Table 9.8-1 and Table 9.8-2 were made. Also, to remove clotting assessment from the blood line and URR. Kt/V assessment was further clarified.	
All	Minor formatting and typographical corrections. One additional reference was added. Additional abbreviations were added to Appendix 1 .	

Clinical Protocol
BMS-986177

CV010010
FXIa

STUDY ACKNOWLEDGMENT/DISCLOSURE

I understand that this protocol contains information that is confidential and proprietary to Bristol-Myers Squibb Company (BMS). Any supplemental information that may be added to this document is also confidential and proprietary to BMS and must be kept in confidence in the same manner as the contents of this protocol.

I have read the original protocol/revised protocol and agree that it contains all necessary details for carrying out the study as described. I will conduct this protocol as outlined therein and will make a reasonable effort to complete the study within the time designated.

I will provide copies of the protocol and access to all information furnished by BMS to study personnel under my supervision. I will discuss this material with them to ensure that they are fully informed about the investigational product and the study.

**Research Hypothesis:**

The purpose of this study is to evaluate the safety profile, tolerability, and pharmacokinetics (PK) of single oral doses of BMS-986177 in ESRD patients undergoing chronic stable HD treatment. Although there is no primary research hypothesis to be formally tested, it is expected that administration of BMS-986177 will prolong the plasma activated partial thromboplastin time (aPTT), reduce plasma FXI clotting activity (FXIc), and have no effect on the prothrombin time and international normalized ratio.

It is expected that the administration of BMS-986177 will prevent clot formation in the extracorporeal HD circuit, hence clotting in the HD filter, lines, and drip chambers will be assessed, additional clotting-related pharmacodynamic (PD) endpoints will be also explored.

**Schedule of Analyses:**

Final analysis will be performed following database lock according to agreed-upon reporting milestone(s), typically after all patients have completed the study.

**2 STUDY DESCRIPTION**

**2.1 Study Design**

This study is a multicenter, cross-over, randomized, open-label trial with blinded endpoint assessment investigating safety and tolerability of single oral doses of BMS-986177 in patients with ESRD undergoing chronic stable HD three times per week. Secondary objectives are to assess BMS-986177 PK and HD success defined as completion of HD without premature interruption of the procedure due to complete clotting of the dialytic circuit and/or filter.

Study treatments will be administered on the first and last HD day of the week (either Monday and Friday, or Tuesday and Saturday, depending on the patients HD schedule), for a total of 4 treatment days (2 doses of BMS-986177, 1 dose of UFH, 1 dose of enoxaparin).

The 2nd HD day of the week is not a study treatment day; on that day, study patients will undergo dialysis with standard of care, as per their schedule, and no study activities will be performed on those days.

Screening for inclusion in the study will be performed up to 28 days before the first study visit. After screening and meeting eligibility as per inclusion and exclusion criteria, patients will be randomized to 1 of 4 sequences that will be conducted in parallel as shown in Table 2.1-1.

**Table 2.1-1 Randomization Scheme**

Sequence No.	Period			
	1	2	3	4
1	UFH	BMS dose 1 (BMS-986177 100 mg)	BMS dose 2 (BMS-986177 300 mg)	Enoxaparin
2	BMS dose 1 (BMS-986177 100 mg)	Enoxaparin	UFH	BMS dose 2 (BMS-986177 300 mg)
3	BMS dose 2 (BMS-986177 300 mg)	UFH	Enoxaparin	BMS dose 1 (BMS-986177 100 mg)
4	Enoxaparin	BMS dose 2 (BMS-986177 300 mg)	BMS dose 1 (BMS-986177 100 mg)	UFH

Study patients will be admitted to the study facility the same day of HD treatment day or the night before. Assessment of vital signs and clinical biochemistry will be performed prior to dosing.

The following study treatments will be administered:

- BMS-986177: 1 single oral dose 3 hours prior to beginning the HD session
- UFH: intravenous infusion to start within 10 minutes prior to beginning the HD session. The dosage and duration of UFH use are at the discretion of the physician and are per their institutional practice
- Enoxaparin: 1 single dose (40 mg) by subcutaneous injection 3 hours prior to beginning the HD session

The HD session will last approximately 4 hours. However, the duration could range from 3 to 4 hours but should be consistent on the days when study treatment is administered. After the HD, patients will remain in the study facility for at least:

- Approximately 3 hours post HD on UFH and enoxaparin treatment days
- Approximately 24 hours post dose on BMS-986177 days

Site staff members blinded to treatment will perform an assessment of clot formation according to criteria set forth in the Clot Formation Assessment Manual which will be provided to the site in a separate document.

Physical examinations (PEs), vital sign measurements, 12-lead electrocardiograms (ECG), and clinical laboratory evaluations will be performed at selected times throughout the dosing interval. Participants will be closely monitored for adverse events (AEs) throughout the study. Blood

samples will be collected for up to 72 hours after study treatment administration for PK analysis and PD analysis. Approximately 365 mL of blood will be drawn from each participant during the study.

The study design schematic is presented in Figure 2.1-1.

**Figure 2.1-1 Study Design Schematic**

		Week 1							Week 2						
Days	D-28 to D-1	D1*	D2	D3	D4	D5‡	D6	D7	D8*	D9	D10	D11	D12‡	D13 to D15	
HD days		1 st HD		2 nd HD		3 rd HD			1 st HD		2 nd HD		3 rd HD		
Study activity	S - E - R	Tx				Tx			Tx				Tx	D	

HD = Hemodialysis session. S= Screening. E = Enrollment. R = Randomization. Tx = Study treatment day (BMS-986177 dose 1 or dose 2, or unfractionated heparin, or enoxaparin). D = Study discharge.

\* D1 and D8 can be Monday or Tuesday depending on the patient's dialysis schedule.

‡ D5 and D12 can be Friday or Saturday depending on the patient's dialysis schedule.

## 2.2 Treatment Assignment

Study treatment will be dispensed at the study visits Days 1, 5, 8, and 12.

Enrolled participants, including those not dosed, will be assigned sequential participant numbers starting with 00001, (eg, 00001, 00002, 00003.... 00010). Sequential numbering may restart at 00001 for each participating site as the distinct patient identification number will ultimately be comprised of the site number and participant number, (eg, 0002 00001). Those enrolled participants meeting inclusion and exclusion criteria will be eligible to be randomized.

Eligible patients will be randomly assigned to 1 of the 4 sequences as listed in Table 2.1-1 in 1:1:1:1 ratio according to a computer-generated randomization scheme. Randomization numbers will be assigned prior to dosing.

Participants will not be replaced if they are discontinued from the study secondary to an AE unless the AE can be determined to be unrelated to treatment. If a participant is replaced after dosing, then the replacement participant will be assigned the original participant's number plus 100. The replacement participant will receive the same treatment as the participant being replaced but a new randomization number will be assigned to him or her. For example, participant 4 would be replaced by Participant 104.

## 2.3 Blinding and Unblinding

This is an open-label study.

## 2.4 Protocol Amendments

This analysis plan reflects Amendment #3 to the protocol, dated 06 September 2017.

### 3 OBJECTIVES

#### 3.1 Primary

The primary objective of this study is to assess safety and tolerability of single oral doses of BMS-986177 in patients with ESRD on chronic HD treatment.

#### 3.2 Secondary

The secondary objectives of this study are to characterize the PK profile of BMS-986177 in a HD population and determine the extent of BMS-986177 on dialytic removal.

[REDACTED]

### 4 ENDPOINTS

#### 4.1 Efficacy Endpoints

There are no planned efficacy endpoints.

#### 4.2 Safety Endpoints

Safety endpoints include incidence of AEs, serious AEs (SAEs), AEs leading to discontinuation, and death as well as marked abnormalities in clinical laboratory tests, ECGs, vital sign measurements, and PEs.

#### 4.3 Pharmacokinetic Endpoints

Pharmacokinetic parameters of BMS-986177 will be derived from the respective plasma concentration versus time data. Individual PK parameter values will be derived by non-compartmental methods by a validated PK analysis program using actual times.

The PK endpoints are Cmax, area under the concentration-time curve (AUC), and dialytic clearance.

The PK parameters to be assessed are shown in Table 4.3-1.

**Table 4.3-1: Pharmacokinetic Parameters, Naming Conventions and Definitions**

Parameter	Definition
C max	Maximum observed plasma concentration
T max	Time of maximum observed plasma concentration
AUC(0-48)	Area under the plasma concentration-time curve from time zero to 48 hours
AUC(0-T)	Area under the plasma concentration time curve from time zero to time of last

**Table 4.3-1: Pharmacokinetic Parameters, Naming Conventions and Definitions**

Parameter	Definition
	quantifiable concentration
AUC(INF)	Area under the plasma concentration time curve from time zero extrapolated to infinite time
T-HALF	Terminal plasma half-life
fu	Fraction of unbound drug
Cmaxfu	Maximum observed plasma concentration of free drug
AUC(0-T)fu	Area under the plasma concentration-time curve from time zero to time of last quantifiable concentration of free drug
AUC(INF)fu	Area under the plasma concentration-time curve from time zero extrapolated to infinite time of free drug
AUC(3-7)	Area under the plasma concentration-time curve from 3 to 7 hours. (i.e., during dialysis. Determined from blood samples entering and exiting the dialyzer)
%DR	Percent dose of BMS-986177 recovered in dialysate (%)
CLD	Dialysate clearance of drug from plasma. Cumulative amount in dialysate over 3 to 7 hours post dose divided by plasma AUC(3-7)

The PK parameters expressed in terms of unbound drug (free drug) concentrations will be derived. The unbound Cmaxfu, AUC(0-T)fu, and AUC(INF)fu for BMS-986177 will be calculated by multiplying the PK parameters of BMS-986177 by the fraction unbound (fu).

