The HD session will last approximately 4 hours. However, the duration could range from 3 to 4 hours but should be consistent on the days when study drug is administered. After the HD, patients will remain in the study facility for at least:

- Approximately 3 hours post-HD on UFH and Enoxaparin treatment days
- Approximately 24 hours post-dose on BMS-986177 days

Site staff members blinded to treatment will perform an assessment of clot formation according to criteria set forth in the Clot Formation Assessment Manual which will be provided to the site in a separate document.

Physical examinations, vital sign measurements, 12-lead electrocardiograms (ECG), and clinical laboratory evaluations will be performed at selected times throughout the dosing interval. Participants will be closely monitored for adverse events throughout the study. Blood samples will be collected for up to 72 hours after study drug administration for pharmacokinetic (PK) analysis and pharmacodynamic (PD) analysis. Approximately 365 mL of blood will be drawn from each participant during the study.

The study design schematic is presented in Figure 5.1-1.

Figure 5.1-1: Study Design Schematic

		Week 1							Week 2						
Days	D-21 to D-1	D1*	D2	D3	D4	D5 [†]	D6	D7	D8*	D9	D10	D11	D12 [†]	D13 to D15	
HD days		1 st HD		2 nd HD		3 rd HD			1 st HD		2 nd HD		3 rd HD		
Study activity	S - E - R	Tx				Tx			Tx				Tx	D	

HD = Hemodialysis session. S= Screening. E = Enrollment. R = Randomization. Tx = Study treatment day (BMS-986177 dose 1 or dose 2, or unfractionated heparin, or enoxaparin). D = Study discharge.

* D1 and D8 can be Monday or Tuesday depending on the patient's dialysis schedule.

† D5 and D12 can be Friday or Saturday depending on the patient's dialysis schedule.

Clinical Protocol
BMS-986177

CV010010
FXIa

Note: Per amendment/revised protocol 01, the BMS-986177 doses will be 100 mg (BMS dose 1) and 300 mg (BMS dose 2).

5.1.1 *Data Monitoring Committee and Other External Committees*

Not Applicable

5.2 **Number of Participants**

Target sample size is 32 participants to achieve 24 participants who completed the 4 study treatments.

5.3 **End of Study Definition**

[figure not shown]

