9.5 Pharmacokinetic

Pharmacokinetics of BMS-986177 will be derived from plasma concentration versus time. The pharmacokinetic parameters to be assessed include:

C _{max}	Maximum observed plasma concentration
T _{max}	Time of maximum observed plasma concentration
AUC(0-T)	Area under the plasma concentration-time curve from time zero to time of last quantifiable concentration
AUC(INF)	Area under the plasma concentration-time curve from time zero extrapolated to infinite time
AUC(0-48)	Area under the plasma concentration-time curve from time zero to 48 hours
T-HALF	Terminal plasma half-life
f _u	Fraction of unbound drug
C _{max} f _u	Maximum observed plasma concentration of free drug
AUC(0-T)f _u	Area under the plasma concentration-time curve from time zero to time of last quantifiable concentration of free drug
AUC(INF)f _u	Area under the plasma concentration-time curve from time zero extrapolated to infinite time of free drug
AUC(3-7)	Area under the plasma concentration-time curve from 3 to 7 hours. (ie, during dialysis. Determined from blood samples entering and exiting the dialyzer)
%DR	Percent dose of BMS-986177 recovered in dialysate (%)
CLD	Dialysate clearance of drug from plasma Cumulative amount in dialysate over 3 to 7 hours postdose divided by plasma AUC(3-7)

Revised Protocol No.: 03

Date: 06-Sep-2017

40

Individual participant pharmacokinetic parameter values will be derived by non-compartmental methods by a validated pharmacokinetic analysis program. Actual times will be used for the analyses.

Table 9.5-1: Pharmacokinetic Sampling Schedule for BMS-986177

Day of Sample Collection when BMS-986177 is dosed	Event	Time Relative to BMS-986177 Dose) Hour: Min	BMS-986177 Blood Sample for PK	BMS-986177 Protein Binding Sample	BMS-986177 Dialysate Sample
BMS-986177 dosing day (depending on randomization sequence it may be study day 1, 5, 8, or 12)	predose	00:00	X ^a		
	postdose	1:00	X		
	hemodialysis start ^c	3:00	X ^b		X (3-7) ^e
		3:30	X ^b		
		4:00	X ^b		
		5:00	X ^b	X	
		6:00	X ^b		
	hemodialysis stop ^c	7:00	X ^b		
		8:00	X		
		9:00	X		
24 to 72 hours after BMS-986177 dosing		24:00 - 72:00 ^d	X		

Note: Day 1, 5, 8, and 12 is the start of Period 1, 2, 3, and 4, respectively. Hemodialysis duration could range from 3 to 4 hours but should be consistent on the days when study drug is administered.

- ^a Sample to be obtained prior to study drug administration.

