- ^b Two blood samples are obtained at each of these time points (one sample is collected prior to entering the dialyzer and the second sample is collected after exiting the dialyzer) for Periods for BMS-986177 only
- ^c Sample to be collected from the blood prior to entering the dialyzer.
- ^d Single sample between days 2-4, days 6-8, days 9-11, and days 13-15.
- ^e Dialysate sample to be collected hourly between 3 to 7 hr during the hemodialysis session.

Clinical Protocol
BMS-986177

CV010010
FXIa

The plasma samples will be analyzed for BMS-986177 by a validated LC/MS/MS assay. In addition, plasma samples will be archived for potential metabolite analysis, if the need arises and to the extent possible.

Detailed instructions for the PK blood collection, labeling, processing, storage, and shipping will be provided to the site in the procedure manual.

After the scheduled PK analyses are completed, residual plasma may be used for metabolite profiling. If these analyses are conducted, they will be reported separately from the CSR.

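### Dialytic clearance (CLD) is written with fixed 3–7 h limits, which match the dialysis session only when it lasts 4 h

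*SAP*

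**What the plan says.** The two documents give the same definition. SAP Table 4.3-1 has "Cumulative amount in dialysate over 3 to 7 hours post dose divided by plasma AUC(3-7" and Protocol 9.5 has "Cumulative amount in dialysate over 3 to 7 hours postdose divided by plasma AUC(3-7". The denominator has its own row in the SAP table: "Area under the plasma concentration-time curve from 3 to 7 hours. (i.e., during dialysis. Determined from blood samples entering and exiting the dialyzer".

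BMS-986177 is given 3 h before dialysis (Protocol 5.1 and 7.1; SAP 2.1). On session length, Protocol 5.1 says "The HD session will last approximately 4 hours", and SAP 2.1 then adds "However, the duration could range from 3 to 4 hours but should be consistent on the days when study treatment is administered". The note under the PK sampling schedule, Protocol Table 9.5-1, repeats the range: "Hemodialysis duration could range from 3 to 4 hours but should be consistent on the days when study drug is administered". That table nevertheless places the end of dialysis at 7:00.

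Footnote e to the table limits dialysate collection to the session: "Dialysate sample to be collected hourly between 3 to 7 hr during the hemodialysis session". On timing, SAP 4.3 says "Individual PK parameter values will be derived by non-compartmental methods by a validated PK analysis program using actual times".

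Dialytic clearance is one of the three PK endpoints named in SAP 4.3. SAP 7.7 summarises CLD by geometric mean and %CV, with no formal test.

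**The concern.** Amount recovered in dialysate divided by plasma AUC is a dialytic clearance only when both terms cover the same stretch of dialysis. With fixed limits of 3 and 7 h, that is so only for a 4 h session. In any shorter permitted session the denominator takes in time off dialysis, when no dialysate is produced. The error always lowers CLD, and more patients would not reduce it.

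There is a second, smaller gap in the same row. It says AUC(3-7) comes from samples on both sides of the dialyzer. Footnote b to Protocol Table 9.5-1 provides for paired samples, and footnote c names the entering side for the start and stop samples. Nothing says which side feeds the CLD denominator.

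At stake is whether a named endpoint, tied to the secondary objective on dialytic removal, can be reproduced. Percent dose recovered, recovery by interval and the safety analyses do not use AUC(3-7).

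**Working it through.** **Does the written window match the session?** Session end = 3 h + duration d.

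- d = 4 h: 3 + 4 = 7 h. The plan's 3–7 h window is reproduced.
- d = 3.5 h: the session ends at 6.5 h.
- d = 3 h: the session ends at 6 h, so 1 h of the 4 h AUC window (25%) lies after dialysis.

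**Can AUC to 7 h still be computed after a 3 h session?** Yes. No dialyzer sample exists at 7 h, but Protocol Table 9.5-1 schedules a sample at 8 h, so software can interpolate to 7 h without raising an error.

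**Size if the limits are taken literally.** The numerator is the same under both readings, so

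literal CLD / session-matched CLD = AUC(3 to 3+d) / AUC(3 to 7).

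The documents give no concentration data, so the profiles are assumptions. For a flat profile the ratio is d/4. For mono-exponential decline it is (1 − e^(−kd)) / (1 − e^(−4k)). The half-life of 9.6 h comes from inclusion criterion 3d in Protocol 6.1, which equates 5 half-lives with 2 days: 48/5 = 9.6 h, and k = ln 2 / 9.6 = 0.0722 per h.

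| Session | Flat | Mono-exponential, 9.6 h |
|---|---|---|
| 3 h | 3/4 = 0.750 (−25.0%) | 0.1947/0.2508 = 0.776 (−22.4%) |
| 3.5 h | 3.5/4 = 0.875 (−12.5%) | 0.2233/0.2508 = 0.890 (−11.0%) |
| 3.75 h | 3.75/4 = 0.938 (−6.3%) | 0.2372/0.2508 = 0.946 (−5.4%) |
| 4 h | 1.000 (0%) | 1.000 (0%) |

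**Sensitivity to the profile.** A one-compartment model was run with these assumed values:

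- half-life 6, 9.6 or 14 h;
- extra dialytic elimination of 0, 0.05 or 0.1 per h during the session only;
- absorption complete by 3 h, or first-order at 0.3, 0.5 or 1.0 per h (slower absorption is included because Protocol 6.3 has dosing after a meal).

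Results:

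- 3 h session: −18.3% to −26.7%.
- 3.5 h session: −8.5% to −13.4%.
- 3.75 h session: −4.1% to −6.7%.

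These are illustrations, not bounds. Absorption at 0.2 per h gives −28.0% for a 3 h session.

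**Check on the samples that would exist.** For a 3 h session, take entering-side samples at 3, 3.5, 4, 5 and 6 h, then the 8 h sample, with 7 h interpolated and the linear trapezoid rule. With a 9.6 h half-life the bias is −22.4% without a dialytic term and −19.7% with 0.1 per h. Log interpolation gives the same.

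**Effect on the reported geometric mean.** If a fraction p of sessions last 3 h and the rest 4 h, the geometric mean is multiplied by r^p, with r between 0.817 and 0.733 (the −18.3% and −26.7% above).

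- p = 0.10: 0.817^0.10 = 0.980 and 0.733^0.10 = 0.969, so 2.0–3.1% low.
- p = 0.25: 0.817^0.25 = 0.951 and 0.733^0.25 = 0.925, so 4.9–7.5% low.

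Both values of p are assumptions.

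**The case against.** The strongest reply is that the text already points to the session. The AUC(3-7) row describes its interval as the dialysis period and says it is built from dialyzer samples. Protocol Table 9.5-1 labels the 7:00 row as the end of dialysis, so 7:00 can be read as a nominal time for a sample tied to that event. Both documents call for actual times. On this reading the stop sample of a 3 h session has an actual time near 6 h, the AUC ends there, and the bias is zero. Reaching 7 h means borrowing the 8 h sample, which is neither during dialysis nor a dialyzer sample.

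That is probably what the authors meant. It does not settle the rule, however. Actual times govern when samples are recorded as taken; they do not move the upper limit of a parameter named and defined as 3 to 7 h. The same table contains AUC(0-48), another partial AUC with fixed limits, so a programmer could reasonably treat 7 h as fixed too.

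SAP 7.10.2 also refers PK analysis to a sponsor harmonization document. It may cover partial-AUC limits, but it is not available here and its content cannot be assumed.

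Other parts of the reply stand. The percentages rest on assumed profiles, sessions are expected to last about 4 h, nothing inferential depends on CLD, and the entering-versus-exiting question is a separate matter to which none of these percentages apply.

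**Conclusion.** The concern holds, as a minor one. As written, CLD is a valid dialytic clearance only for a 4 h session. For a permitted 3 h session, the fixed limits understate it by roughly 18–27% under the profiles assumed here; with session-matched limits there is no bias. Because the documents give no distribution of session lengths, the effect on the summary cannot be pinned down and may be small: 2–3% on the geometric mean if a tenth of sessions last 3 h, and 5–8% if a quarter do. The within-patient comparison of 100 mg with 300 mg is largely protected, since session length should be consistent across study days. What remains is an endpoint definition that allows two different answers from the same shorter session, one of them biased in a known direction.

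**What to change.** In SAP Table 4.3-1, define CLD as the cumulative amount recovered in dialysate from actual dialysis start to actual dialysis stop, divided by the plasma AUC over that same interval, computed from samples entering the dialyzer. Keep AUC(3-7) only as a nominal label and say so in its row. Bring the definition in Protocol 9.5 into line.

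It would help to state in the same place how CLD is derived when a session is cut short by clotting and perhaps restarted, which Protocol 8.1 foresees. A session stopped at 2 h and not restarted would give a literal CLD 50% low with a flat profile (2/4) and 46% low at the 9.6 h half-life (0.1345/0.2508 = 0.536).

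The cost is wording, before database lock. The hourly dialysate and entering-side samples are already scheduled. Session duration is already listed as part of the Kt/V assessment (Protocol Appendix 1), but that entry does not show that start and stop clock times are recorded, so actual times must be carried into the PK dataset. Changing the protocol text brings the ethics-committee steps in Protocol Appendix 2; the SAP change alone would fix the calculation.
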